1.4.1. Inclusion Criteria

Study participants meeting all of the following criteria will be allowed to enroll in the study:

1. Males and females ages 18 to 60 years old, inclusive, at the Screening Visit.
2. ALS diagnosed as possible, laboratory-supported probable, probable, or definite as defined by revised El Escorial criteria.
3. Having onset of ALS disease symptoms, including limb weakness within 24 months at the Screening Visit.
4. ALSFRS-R ≥ 25 at the screening visit.
5. Upright Slow Vital Capacity (SVC) measure $\geq 65\%$ of predicted for gender, height, and age at the Screening Visit (See [Appendix 3](#)).
6. Decline in ALSFRS-R total score of 3 or more points in the 12 weeks preceding randomization.
7. Participants must be taking a stable dose of riluzole, or no riluzole at all (riluzole-naïve participants are permitted in the study), for at least 30 days prior to the Screening Visit and be willing to maintain the riluzole dose for the duration of the study.
8. Women of childbearing potential shall either be surgically sterile, or must agree not to become pregnant for the duration of the study. Women must be willing to undergo a serum pregnancy test at screening, one week before bone marrow aspiration, at the visit prior to each MSC-NTF transplantation and at the conclusion of the study. Participants

of childbearing potential must agree to use a medically approved form of birth control (abstinence, intrauterine device (IUD), oral contraception, barrier and spermicide or hormonal implant) throughout the duration of the study and for at least 3 months following the last transplantation. For those women who are sexually active and using oral contraceptives, a second form of barrier contraception is required. Men must be willing to consistently use two forms of contraceptive if their partners are of childbearing age.

9. Capable of providing informed consent and willing and able to follow study procedures, including willingness to undergo multiple/repeated lumbar puncture.
10. Geographic accessibility to the study site and willingness and ability to comply with follow-up.
11. Citizen or permanent resident of the US or Canadian citizen able to travel to a US site for all follow-up study visits

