1.5. STUDY ASSESSMENTS

The SOA provides a visual listing of study assessments at each visit.

The study assessments at each visit are provided in Table 1 in [Appendix 1](#). The timing of the key study visits, Randomization (V4), BMA (V5), T1 (V6), T2 (V9) and T3 (V11) that are driven by manufacturing availability, may require a more flexible window to align with the manufacturing slot allocated to the individual participant.

The study manual with details of assessments are provided in [Appendix 2](#) (ALSFRS-R) [Appendix 3](#) (SVC) and [Appendix 4](#) (C-SSRS).

This is a multicenter study. The Sponsor will ensure that all medical centers will be performing study assessment procedures in the same way by providing appropriate training to sites.

Any evaluator performing ALSFRS-R assessments will be trained and certified. ALSFRS-R assessments will be done in person at in-clinic visits. If an ALSFRS-R cannot be provided in-person it will be administered via the telephone. The ALSFRS-R has been validated for administration over the phone ([Kasarski EJ et al 2005](#), [Mannino M et al 2007](#)).

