1.5.4.4. Visit 5: Bone Marrow Aspiration Visit

At Visit 5 (Week-5-6, coordinated with patient-assigned manufacturing slots), all participants consenting to participate in the study and meeting the eligibility criteria who have been randomized at Visit 4 (Week -5) will undergo bone marrow aspiration. The bone marrow aspiration (BMA) procedure will be performed by a credentialed health care provider as per Medical Centre procedures from multiple punctures of the iliac crest of the participants' pelvic bone. Participants will also undergo the following assessments:

- Review of concomitant medications
- Vital sign measurements (including blood pressure, body temperature; pulse and respiration rate after sitting for at least 3 minutes)
- Review of Adverse events
- Bone Marrow Aspiration

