1.5.5 Transplantation Visits

1.5.5.1. Visit 6 (T1): 1st Cell Transplantation (Day 0- up to Day 3)

At the 1st transplantation visit, approximately 5-6 weeks from BMA, coordinated with patient-assigned manufacturing slots, participants will be admitted to an inpatient study unit for study procedures. Pre-transplant assessments will include:

- Admit to Inpatient Ward
- Body weight (in pounds) measurement
- Directed physical examination
- Vital sign measurements (including blood pressure, body temperature; pulse and respiration rate after sitting for at least 3 minutes)
- ALSFRS-R questionnaire
- SVC pulmonary function test
- Neurological examination
- Review of concomitant medications
- Blood for hematology, coagulation, biochemistry, and biomarker evaluations; as well as urinalysis will be collected
- Review of adverse events
- Standard 12-Lead ECG

Following pre-transplant procedures, participants will undergo (Hr. 0 - Estimated Time 12:00-14:00):

- Immediately prior to the IT administration of cells or placebo, CSF will be removed and retained for analysis.

- IT injection of cells or placebo by an un-blinded team/physician.

Concomitant medications and AEs will be monitored throughout the study visit, as necessary.

Post-transplant procedures, participants will undergo the following:

- Vital signs will be monitored at 2, 4 (\pm 15 mins.), 7, 20, and 24 hours (\pm 30 mins.) post-transplant and/or upon discharge at approximately 24 hours or up to 72 hours post transplantation. Inpatient observation is up to 72 hours, with earlier discharge at investigator discretion.
- Visual inspection of the injection site will be performed at 2 (\pm 15 mins.), and 20 (\pm 30 mins.) hours post-transplant.
- Directed physical examinations will be performed upon discharge (at up to 72 hours post transplantation).
- Blood for hematology, coagulation, biochemistry, and biomarker evaluations, as well as urinalysis will be collected 20 hours (\pm 30 mins.) post-transplant.

Prior to discharge, assessments will include:

- Vital sign measurements (including blood pressure, body temperature; pulse and respiration rate after sitting for at least 3 minutes)
- Directed physical examinations will be performed at approximately 24 hours or up to 72 hours post transplantation).
- Review of concomitant medications
- Review of adverse events
- Assessment of blinding (subject and investigator)
- Discharge from Inpatient Setting

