1.5.5.3. Visit 8: Week 4 (\pm 3 days) Follow-Up

At the Week 4 follow-up visit, participants will undergo:

- Review of concomitant medications
- Review of adverse events
- Vital sign measurements (including blood pressure, body temperature; pulse and respiration rate after sitting for at least 3 minutes)
- Directed physical examination, including weight
- Neurological examination
- ALSFRS-R questionnaire
- Blood collection for biomarker evaluation.
- Lumbar puncture and collection of CSF.
- Serum pregnancy test (female participants)

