1.15. APPENDICES

1.15.1. Appendix 1: Listing of study activities

1.15.1.1. Scheduled monitoring events

Table 1 Schedule of Assessments:

Study Period	Pre-treatment period					Cells/Placebo Transplantation period						Post-transplantation follow-up		
	Screening period													
Visit	V1	V2	V3	V4 ¹	V5	V6	V7	V8	V9	V10	V11	V12	V13	V14 ¹²
Procedure	Screening	ALSFRS-R Assessments		Randomization	BMA	Cell Transplantation (T1)			Cell Transplantation (T2)		Cell Transplantation (T3)			
Time Schedule	Week -18-20 (± 7 days)	Week -14 to-16 (± 7 days)	Week -10 to -12 (± 7 days)	Week -6 to-9	Week -5 to -6 ¹⁰	Day 0 - Day 3 ¹¹	Week 2 (± 3 days)	Week 4 (± 3 days)	Week 8 ¹¹ (± 5 days)	Week 12 (± 5 days)	Week 16 ¹¹ (± 5 days)	Week 20 (± 5 days)	Week 24 (± 5 days)	Week 28 (± 5 days)
Informed consent	√													
Eligibility criteria	√			√										
Demographic data	√													
Height	√													
Body weight	√		√			√		√	√	√	√	√	√	√
Physical examination	√					√		√	√	√	√	√	√	√
12 lead ECG	√					√			√		√			
Vital signs ²	√	√	√	√	√	√	√	√	√	√	√	√	√	√
Medical History	√													
ALS Medical History ³	√													

Study Period	Pre-treatment period					Cells/Placebo Transplantation period						Post-transplantation follow-up		
	Screening period													
Visit	V1	V2	V3	V4 ¹	V5	V6	V7	V8	V9	V10	V11	V12	V13	V14 ¹²
El Escorial Criteria	√													
ALSFRS-R ⁴	√	√	√	√		√	√	√	√	√	√	√	√	√
Neurological Examination	√			√		√	√	√	√	√	√	√	√	√
Slow Vital Capacity (SVC)*	√					√			√		√			√
Prior/Concomitant medication review	√	√	√	√	√	√	√	√	√	√	√	√	√	√
HIV 1 and 2	√			√										
HBV	√			√										
HCV	√			√										
Pregnancy test (for women with childbearing potential)	√			√				√		√				√
Hematology ⁵	√			√		√			√		√		√	√
Blood biochemistry ⁶	√			√		√			√		√		√	√
Coagulation tests ⁷	√			√		√			√		√			
Blood collection for biomarkers ⁸						√	√	√	√	√	√	√		
Urinalysis ⁹	√			√		√			√		√		√	√
Bone marrow aspiration					√									
Transplant (IT)						√			√		√			
CSF collection						√	√	√	√	√	√	√		
Visual inspection of injection site						√			√		√			

Study Period	Pre-treatment period					Cells/Placebo Transplantation period						Post-transplantation follow-up		
	Screening period													
Visit	V1	V2	V3	V4 ¹	V5	V6	V7	V8	V9	V10	V11	V12	V13	V14 ¹²
Adverse events review		√	√	√	√	√	√	√	√	√	√	√	√	√
C-SSRS	√										√			√
Assessment of blinding (Subject, Investigator and person doing ALSFRS-R assessments)						√								√

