- 12 An ET visit will be conducted only for participants who discontinue the study after treatment, post Visit 6. The ET visit will include all the procedures required at study Visit 14. For participants who refuse further clinic study visits, telephone contact by study staff shall be attempted and documented to review for adverse events at each scheduled visit through the remainder of study.

Table 2 Detailed Schedule of Assessments for Cell Transplantation Visits (V6, V9 and V11)

Estimated Time	06:00-14:00	12:00-14:00	14:00-16:00	16:00-18:00	19:00-21:00	08:00-10:00	12:00-14:00	
Time\ Procedure	Up to 6 hours before transplant	Hr. 0	Hr. 2 (±15 min)	Hr. 4 (±15 min)	Hr. 7 (±30 min)	Hr. 20 (±30 min)	Approximately Hr. 24 (±30 min)	Hr. ≥ 24-72 (before discharge ±30 min)
Admit to Inpatient Ward	√							
Body weight	√							
Physical Examination	√						√	
Vital signs ¹	√		√	√	√	√	√	√
12 lead ECG ²	√ ²						√ ²	
ALSFRS-R	√							
Slow Vital Capacity (SVC)*	√							
Neurological Examination	√							
Concomitant medication review ³	√		√	√	√	√	√	√
Hematology ⁴	√					√		
Blood biochemistry ⁵	√					√		
Urinalysis ⁶	√					√		
Coagulation ⁷	√					√		
Blood collection for biomarkers ⁸	√					√		
Cell Transplant IT ⁹		√						
Retention of CSF sample		√						
Visual inspection of injection site			√			√ ⁹		
Adverse events review ³	√		√	√	√	√	√	√
C-SSRS ¹⁰	√							
Assessment of blinding (Participant and Investigator) ¹¹								√
Discharge from Inpatient Setting								√

Brainstorm Cell Therapeutics		
Phase 3 Clinical Protocol BCT-002 US Amendment 2.1: March 2020	NurOwn® (MSC-NTF cells)	Page 62 of 66

Abbreviations: ALS=Amyotrophic Lateral Sclerosis; ALFRS-R=ALS Functional Rating Scale–Revised; CSF=cerebral spinal fluid; C-SSRS=Columbia-Suicide Severity Rating Scale ECG=electrocardiogram; IT=intrathecal

* SVC will be performed when permitted, following resolution of COVID-19 per institutional guidance

- 1 Pulse rate, Blood pressure, Respiratory rate, Body temperature at the designated time-points. At 2, and 4 hours \pm 15 minutes. At 8, 20 and 24 hours \pm 30 minutes
- 2 ECG will be performed at Visits 6, 9 and 11 – Time Window: +/- 30 min.
- 3 Concomitant medications and AEs will be monitored and ongoing data will be collected throughout the study visit, as necessary
- 4 Hematology: Complete blood count (Red blood cells with Indices, white blood cells with differential and platelet count, hemoglobin, hematocrit) - Time Window: +/- 30 min.

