**Table 3: Detailed Schedule of Assessments for Cell Transplantation Visits (V6, V9 and V11)**

Estimated Time	06:00-14:00	12:00-14:00	14:00-16:00	16:00-18:00	19:00-21:00	08:00-10:00	12:00-14:00	
Time\ Procedure	Up to 6 hours before transplant	Hr. 0	Hr. 2 (±15 min)	Hr. 4 (±15 min)	Hr. 7 (±30 min)	Hr. 20 (±30 min)	Approximately Hr. 24 (±30 min)	Hr. ≥ 24-72 (before discharge ±30 min)
Admit to Inpatient Ward	√							
Body weight	√							
Physical Examination	√						√	
Vital signs 	√		√	√	√	√	√	√
12 lead ECG 	√						√ 	
ALSFRS-R	√							
Slow Vital Capacity (SVC)	√							
Neurological Examination	√							
Concomitant medication review 	√		√	√	√	√	√	√
Hematology 	√					√		
Blood biochemistry 	√					√		
Urinalysis 	√					√		
Coagulation 	√					√		
Blood collection for biomarkers 	√					√		
Cell Transplant IT 		√						
Retention of CSF sample		√						
Visual inspection of injection site			√			√ 		
Adverse events review 	√		√	√	√	√	√	√
C-SSRS 	√							
Assessment of blinding (Participant and Investigator) 								√
Discharge from Inpatient Setting								√

Abbreviations: ALS=Amyotrophic Lateral Sclerosis; ALFRS-R=ALS Functional Rating Scale–Revised; CSF=cerebral spinal fluid; C-SSRS=Columbia-Suicide Severity Rating Scale ECG=Electrocardiogram; IT=Intrathecal

- 1 Heart rate, Blood pressure, Respiration rate, Body temperature at the designated time-points. At 2, and 4 hours  $\pm$  15 minutes. At 8, 20 and 24 hours  $\pm$ 30 minutes.
- 2 ECG will be performed at Visits 6, 9 and 11 – Time Window: +/- 4 hours.
- 3 Concomitant medications and AEs will be monitored, and ongoing data will be collected throughout the study visit, as necessary.
- 4 Hematology: Complete blood count (Red blood cells with Indices, white blood cells with differential and platelet count, hemoglobin, hematocrit) - Time Window: +/- 30 min.
- 5 Blood Biochemistry: Sodium, Potassium, Calcium, Bicarbonate, blood urea nitrogen, Creatinine, Glucose, Chloride, Magnesium, Phosphorus, total protein, triglycerides, Total cholesterol, high-density lipoprotein, low-density lipoprotein, urea, total bilirubin, aspartate aminotransferase (glutamic oxaloacetic transaminase), alanine aminotransferase (glutamic pyruvic transaminase), alkaline phosphatase, uric acid - Time Window: +/- 30min.

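### The protocol names a pregnancy test at the visit before each transplantation, but none is scheduled at Visit 5, before the first; a test there would gain about one week over Visit 4

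*Protocol*

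**What the plan says.** Criterion 8 in Protocol section 1.4.1 lists the testing occasions that women must be willing to undergo: screening, then "one week before bone marrow aspiration, at the visit prior to each MSC-NTF transplantation and at the conclusion of the study". The test before aspiration and the test before each transplantation are separate items.

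Protocol section 1.5 directs sites to the schedule: "The study assessments at each visit are provided in Table 1". In that table the row "Pregnancy test (for women with childbearing potential") is ticked at Visits 1, 4, 8, 10 and 14. SAP Table 2 has the same five ticks. The visit texts agree. For example, the Visit 8 list (section 1.5.5.3) includes "Serum pregnancy test (female participants"), and Visit 10 (section 1.5.5.5) has the same entry.

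The Visit 5 list (section 1.5.4.4) has concomitant medications, vital signs, adverse events and the aspiration. For laboratory work before the injection, the Visit 6 list (section 1.5.5.1) has "Blood for hematology, coagulation, biochemistry, and biomarker evaluations; as well as urinalysis will be collected", with no pregnancy test. Protocol Table 2 and SAP Table 3, which detail the transplantation days, have no pregnancy row.

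**The concern.** A site that follows Table 1 will give the first dose without the pre-transplantation test that the protocol itself names, although the second and third doses each have one. A woman who conceives after Visit 4 could receive T1 untested. Section 1.3.3.2 makes the second and third treatments conditional on there being no medical contraindication, but it does not say this for the first. The gap therefore sits at the first exposure to the product, where the interval since the last test is nominally the longest of the three. What is at stake is participant safety and consistency between protocol text and schedule, not inference.

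**Working it through.** **Step 1. Tests named against tests scheduled.** The transplantations are at Visits 6, 9 and 11 (section 1.3.1).

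| Transplantation | Visit before it | Test scheduled there? |
|---|---|---|
| T1, Visit 6 (Week 0) | Visit 5 | No |
| T2, Visit 9 (Week 8) | Visit 8 | Yes |
| T3, Visit 11 (Week 16) | Visit 10 | Yes |

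Visit 4 cannot stand in as the visit before T1. Visit 5 lies between them, and criterion 8 lists the pre-aspiration test as a separate item. For T2 and T3 the schedule uses the immediately preceding visit.

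**Step 2. Interval from the last test (Visit 4) to T1.** The sources differ:

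- Protocol Table 1 and section 1.5.4.3, Week -6 to -9: 6-9 weeks, or 42-63 days.
- SAP Table 2, Week -6 to -7: 6-7 weeks, or 42-49 days.
- Section 1.3.4 (randomization one week before aspiration) plus section 1.5.5.1 (T1 about 5-6 weeks after aspiration): 1 + 5 = 6 to 1 + 6 = 7 weeks.
- Section 1.3.1 and SAP section 4.1, Week -5: about 5 weeks, or 35 days.

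**Step 3. Same interval for T2 and T3.**

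- T2: 56 - 28 = 28 days. The windows add 3 + 5 = 8 days either way, giving 20-36 days.
- T3: 112 - 84 = 28 days. The windows add 5 + 5 = 10 days either way, giving 18-38 days.

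The 42-day minimum for T1 in both schedule tables exceeds the upper ends of 36 and 38 days. The 35-day figure from section 1.3.1 does not. Table 1 footnote 11 allows wider windows for manufacturing reasons, which could lengthen any of these intervals.

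**Step 4. What the missing Visit 5 test would have gained.**

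- Visit 5 to T1: 5-6 weeks (both schedule tables and section 1.5.5.1) or 4 weeks (section 1.3.1 and SAP section 4.1), so 4-6 weeks overall.
- Gain over Visit 4 on the stated spacing: 1 week (section 1.3.4; also 5 - 4 = 1 from section 1.3.1).
- Gain on the Table 1 windows: minimum 6 - 6 = 0 weeks, maximum 9 - 5 = 4 weeks.

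Step 4 measures the mismatch. Step 2 describes the resulting interval, most of which a compliant Visit 5 test would leave in place.

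**The case against.** The best textual defence is Protocol section 1.5.4 (Clinical Laboratory Safety Tests), which names serum hCG under a heading that covers Visits 1, 4, 6, 9, 11, 13 and 14. Read alone, it would put a test at Visit 6. It does not close the gap, because it defers to the Schedule of Assessments, which has no Visit 6 test. It also omits Visits 8 and 10, where tests are scheduled, and includes Visits 9, 11 and 13, where none is. It is a general laboratory list, and Visit 6 would in any case not be the visit before T1.

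Two other defences stand in part. First, criterion 8 is about willingness, so a missing test makes no participant ineligible. Exclusion 17 (pregnancy) is checked by the tests at Visits 1 and 4. Second, the investigator may discontinue a participant for any appropriate reason (section 1.8.5.2), and examination and adverse-event review precede the T1 injection, so a known pregnancy could be acted on. Neither supplies the test that would reveal an unrecognized pregnancy.

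A reader might infer that the error costs 6-9 weeks of untested time, or that the protocol calls for a test on the day of dosing. The documents support neither. Criterion 8 asks only for the preceding visit, and even for T2 and T3 the test falls about four weeks before the dose.

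**Conclusion.** The mismatch is real but minor. The test named for the visit before T1 appears at no visit, and the schedule tables and visit texts agree on its absence. The interval from the last test to T1 is 6-9, 6-7 or about 5 weeks, depending on the source. Full compliance would shorten it by about 1 week, or by 0-4 weeks on the Table 1 windows.

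The safety benefit is small, given mandatory contraception (criterion 8), two earlier tests and the pregnancy reporting rules (section 1.8.3). No endpoint or analysis is affected; SAP section 7.7 only lists pregnancy results by participant. The practical value also depends on how many women had yet to reach Visit 6. Section 1.5.3 shows that some participants had already completed or discontinued, and the documents give no count. If no woman remained, only the inconsistency in wording is left.

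**What to change.** **Primary change**, for women of childbearing potential:

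1. Tick Visit 5 in the pregnancy row of Protocol Table 1 and SAP Table 2.
2. Add a serum pregnancy test to the Visit 5 list in section 1.5.4.4.
3. State in the protocol that T1 is not given if the result is positive.

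This meets criterion 8 as written, and the central laboratory named in section 1.11 can run the test. The cost is one small blood sample at Visit 5, where no blood draw is now listed, one central-laboratory test per woman, and a protocol amendment with IRB approval (section 1.12.1).

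**Optional stronger version.** Test the blood already drawn before the Visit 6 injection, with a local result inside the pre-transplant period that Protocol Table 2 labels "Up to 6 hours before transplant". This brings the interval down to the same day. It goes beyond anything the documents ask for and needs more edits:

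- reword criterion 8;
- exempt this test from central analysis in section 1.11;
- tick Visit 6 in Protocol Table 1 and SAP Table 2;
- add a Visit 6 pre-transplant row to Protocol Table 2 and SAP Table 3;
- put the test and the withholding rule in section 1.5.5.1, or the rule in section 1.3.3.2.

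A positive result would mean a discarded syringe (section 1.12.3) and a randomized woman left untreated. If she is never treated, she falls outside the mITT population used for the SAP primary analysis (SAP sections 6.5.2 and 8.3.1). A positive Visit 5 result could have the same consequence for that population.

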1.4.2. Exclusion Criteria

Study participants meeting any of the following criteria during screening evaluations will be excluded from entry into the study:

1. Prior stem cell therapy of any kind.
2. Active participation in any other ALS interventional study
3. Inability to lie flat for the duration of intrathecal cell transplantation and/or bone marrow biopsy, or inability to tolerate study procedures for any other reason.
4. History of autoimmune disease that may confound study results myelodysplastic or myeloproliferative disorder, leukemia or lymphoma, whole body irradiation, hip fracture, or severe scoliosis. If in doubt, the subject's eligibility should be discussed with the medical monitor.
5. Any unstable clinically significant medical condition other than ALS (e.g., within six months of baseline, had myocardial infarction, angina pectoris, and/or congestive heart failure), treatment with anticoagulants that, in the opinion of the investigator, would compromise the safety of participants.
6. Any history of malignancy, within the previous 5 years, with the exception of localized skin cancers (with no evidence of metastasis, significant invasion, or re-occurrence within three years of baseline).
7. Serum AST or ALT value >3.0 times the upper normal limit.
8. Serum creatinine value >2.0 times the upper normal limit.
9. Positive test for Hepatitis B, Hepatitis C, HIV.
10. Current use of immunosuppressant medication or use of such medication within 4 weeks of Screening visit (Visit 1).
11. Any history of acquired or inherited immune deficiency syndrome.

12. Use of RADICAVA (edaravone injection) within 30 days of screening or intent to use RADICAVA at any time during the course of the study including the follow up period.
13. Exposure to any other experimental agent (off-label use or investigational) or participation in a clinical trial within 30 days prior to Screening Visit (Visit 1).
14. Use of non-invasive ventilation (NIV), diaphragm pacing system or invasive ventilation (tracheostomy) at the screening or randomization visit.
15. Any history of either substance abuse within the past year, or unstable psychiatric disease according to PI judgment.
16. Usage of feeding tube at screening or the randomization visit.
17. Pregnant women or women currently breastfeeding.

